## Tremor amplitude using IMU data

Tremor amplitude is measured during the performed tasks by taking the data from the IMU that is attached to the fingers. Likewise, this endpoint score will be compared over the two conditions using two-tailed matched pairs t-test, to analyze the difference in tremor amplitude. Again, the data will be checked for normal distribution, and the effect of the sham device will be evaluated.

The mean reduction in tremor severity according to both TETRAS rating and tremor amplitude of the hand are the co-primary endpoints. Sub analyses will be performed to evaluate the effect of the orthosis on these endpoints during the different tasks. This will be done to analyze the effect of the orthosis on specific tremor types: kinetic tremor (eating, drinking, pouring and spiral drawing), postural tremor (forward outstretched posture, lateral wing beating posture) and intention tremor (finger-to-nose).

## 9.2 Secondary study parameter(s)

## Patient satisfaction using D-QUEST

The secondary study parameter 'patient's satisfaction' will both be assessed after the sham device and anti-tremor orthosis with the D-QUEST questionnaire. A sub-analysis per question will be performed, depicting the percentages of the total amount of patients that belong to one categorical measure (e.g., *very satisfied, not satisfied*).

#### Potential adverse effects

All potential adverse effects – obtained from both the AEs reported from by investigator and subquestions in D-quest – will be listed with their prevalence per patient (e.g. 15% of participants displayed skin marks).

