## 2.2 Secondary Objectives

Apart from performance objectives, the intervention with the orthosis shall also be assessed on usability and comfort and safety with two primary objectives:

- 1. To assess patient satisfaction with regards to the usability and comfort of the STIL antitremor orthosis.
- 2. To assess possible adverse effects of the STIL anti-tremor orthosis.

The endpoint of the first secondary objective is the Dutch version of the Quebec user evaluation of satisfaction with assistive technology (D-QUEST) questionnaire, providing a subjective outcome of the usability and comfort of the orthosis from the patient's perspective. The endpoint of the second secondary objective is a listing of (possible) adverse effects, observed either by the investigator and noted down in a (S)AE report form, or as mentioned by the patient in de D-QUEST questionnaire.

Together, the secondary endpoints provide an assessment on safety, comfort and usability of the device.

The health-related quality of life (QoL) will also be evaluated, as this could influence satisfaction from the secondary objective.

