## 7.3.5 Cross-over test procedure

The study is designed to be a cross-over study, where baseline is compared to the intervention, and sham is also compared to the intervention.

The assessment procedure in Sections 7.3.3 and 7.3.4 will therefore be repeated 3 times, like is depicted in Figure 4.

The first condition is the baseline condition without orthosis. In the second and third condition, the sham device and anti-tremor orthosis will be tested, in randomized order. The CRF software determines the randomization.

The investigator will fasten the orthosis as explained in Section 6.5. The IMU sensors can stay attached at the same places as in the baseline condition.

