## 7.3.7 Reporting Adverse Events

During the entire visit, the principal investigator will report every observed adverse event using the Adverse Event (AE) Report Form. This form will specify the severity, relation to the study intervention, the taken action, the outcome, the expectancy and whether the event was a SAE of the AE. If SAEs have been observed, they must be reported by the sponsor

though the web portal of *ToetsingOnline*, more information can be found in Section 8.

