## 8.2 AEs and SAEs

## 8.2.1 Adverse events (AEs)

Adverse events are defined as any undesirable experience occurring to a subject during the study, whether or not considered related to the investigational product or trial procedure. All adverse events reported spontaneously by the subject or observed by the investigator or his staff will be recorded using the *Adverse Event (AE) report form* (Dutch: meldingsformulier) that can be found in Appendix II.

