## Adverse Event (AE) Meldingsformulier

#### ONDERDRUKKING VAN ONDERARM TREMOR MET DE STIL ANTI-TREMOR ORTHESE

Protocol ID: \_\_\_\_\_ Dit formulier is cumulatief en legt de bijwerkingen van een enkele deelnemer tijdens het onderzoek vast.

Ernst	Relatie met de studie interventie	Ondernomen actie betreft interventie	Resultaat van AE	Verwacht	Serious Adverse Event (SAE)
2 = Matig 3 = Ernstig 4 = Levens- bedreigend	2 = Onwaarschijnlijk 3 = Mogelijk 4 = Waarschijnlijk 5 = Zeker	1 = Dosisaanpassing 2 = Medische interventie 3 = Ziekenhuisopname 4 = Interventie stopgezet 5 = Anders	2 = Hersteld met kleine gevolgen 3 = Hersteld met grote gevolgen 4 = Waarschijnlijk 5 = Doorgaan bebandeling	2 = Nee	2 = Nee (Indien ja, melden via ToetsingOnline )
			Verslechtering van toestand 6 = Dood 7 = Onbekend		

Alleen aan het einde van de studie: Vink dit vakje aan als de deelnemer geen bijwerking had 🗌 Geen

Adverse event	Ernst	Relatie	Ondernomen actie	Resultaat van AE	Verwacht?	SAE?

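### The adverse event form has no field for the device worn or the time of onset, and Section 9.2 gives prevalence per patient without a device split, so investigator-recorded events cannot be reliably assigned to orthosis or sham

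*Protocol*

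**What the plan says.** - **Objective.** Protocol Section 2.2 states the second secondary objective as "To assess possible adverse effects of the STIL anti-tremor orthosis". It names one device.
- **Exposure.** Section 7.3.5 puts baseline first and continues: "In the second and third condition, the sham device and anti-tremor orthosis will be tested, in randomized order". Section 3 places both devices in the same appointment.
- **Recording.** Section 8.2.1 routes events to one form: "All adverse events reported spontaneously by the subject or observed by the investigator or his staff will be recorded using the" adverse event form of Appendix II. Section 7.3.7 lists its content: "This form will specify the severity, relation to the study intervention, the taken action, the outcome, the expectancy" and whether the event was serious.
- **The form.** Appendix II describes itself in Dutch: "Dit formulier is cumulatief en legt de bijwerkingen van een enkele deelnemer tijdens het onderzoek vast". That is, one cumulative sheet per participant for the whole study. Its columns are event, severity, relation, action, outcome, expected and SAE. The relation column is headed "Relatie met de studie interventie" (relation to the study intervention).
- **Analysis.** Under Potential adverse effects, Section 9.2 draws on two sources, "obtained from both the AEs reported from by investigator and subquestions in D-quest", and says the effects "will be listed with their prevalence per patient (e.g. 15% of participants displayed skin marks".
- **Second source.** Section 7.3.6 has D-QUEST completed after the sham and again after the orthosis. Section 7.1.2 adds sponsor questions to it that cover possible adverse effects.

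**The concern.** The objective asks about the orthosis, but the form records events over a visit that includes a period with no device, a sham period and an orthosis period, without saying in which period the event arose. A patient with redness or muscle pain on the form could have had it from either device.

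This is the first clinical study of the orthosis in patients, and Section 10.4 says that no facts about its risks are yet known. The sham has a similar look and weight but no dampers (Section 5.1). A tabulation by device would therefore help to distinguish effects of fit and weight, which either device can produce, from effects of damping, which only the orthosis can produce. The form as designed does not secure the data for that tabulation.

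A statistical analysis plan could add a column to a table. It could not restore a variable that was not collected at the visit.

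**Working it through.** **1. Does any required record name the device for an event?**

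| Record | Where | Device or timing for an adverse event? |
|---|---|---|
| Adverse event form | Appendix II; fields also in 7.3.7 | No device, condition, period or onset column |
| Relation column | Appendix II | Refers to the study intervention; no device named. Section 7.1.2 describes it as relationship to the study |
| Digital CRF and investigator notes | 7.2, 11.1.2 | Data are filed under the device variant and notes are logged, but no device entry is required for an adverse event |
| Device accountability log | Appendix III | Device type, patient ID and date of use; no clock time and no link to events. Both devices share a date |
| D-QUEST and added questions | 7.1.2, 7.3.6 | Yes: completed after each device |

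So the questionnaire source can be split by device from data already planned. The form source can be split only if someone happens to note the device.

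The missing columns are unlikely to be a loss in text extraction, because the prose list in Section 7.3.7 matches the form and also has no device or timing item.

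**2. What can a per-patient prevalence say about the orthosis?**

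Let P be the proportion of patients with the event on at least one device, made up of orthosis only, sham only, and both. Then

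orthosis rate = P(orthosis only) + P(both) = P − P(sham only).

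P(sham only) can lie anywhere from 0 to P, so the orthosis rate can lie anywhere from 0 to P. Any baseline events counted in P leave P an upper bound.

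Input: the 15% in Section 9.2, which is the protocol's example and not an expected rate.

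- All events on the orthosis: 15% − 0% = 15%.
- All events on the sham only: 15% − 15% = 0%.
- Equal and independent rates p on each device (an assumption): 1 − (1 − p)² = 0.15, so p = 1 − √0.85 = 0.078, or 7.8%.

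**3. The same in whole patients.**

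Assume 4 of the planned 25 patients have the event on at least one device: 4/25 = 16%. The number of ways to divide 4 patients into orthosis only, sham only and both is (6 × 5)/2 = 15. Across these the orthosis rate runs from 0/25 = 0% to 4/25 = 16%, and the orthosis-minus-sham difference from −16 to +16 percentage points. Without the device, the data do not even fix the direction of the difference.

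**The case against.** **The questionnaire is already specific to the device.** A reader might infer that orthosis and sham effects cannot be separated at all. The documents do not support that: patients answer after each device, and the added questions ask about adverse effects. This stands, and it confines the problem to events observed by the investigator or reported spontaneously. Some effects, such as skin marks, may be captured by both routes.

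**Section 9.2 does not say that the devices are combined.** Prevalence per patient fixes the denominator, and a breakdown by condition is the kind of detail an analysis plan may supply. This also stands: pooling is inferred from the absence of a split. It does not answer the missing field on the form.

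**The relation column may already mean the orthosis.** Section 7.2 uses the word intervention for the orthosis as opposed to the sham, and Appendix III contrasts sham with intervention. The investigator knows which device is on, so an attribution at the time is possible. In part this stands. However, the column is a graded causality judgement, its heading does not name a device, and an event rated unrelated leaves open which device was worn.

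**The information may exist elsewhere.** CRF notes or the free-text event column might mention the device. It is therefore too strong to say that the device is never recorded; what holds is that nothing requires it.

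**The sham was not introduced as a safety control, and an upper bound is conservative.** Sections 5.1 and 7.2 give its purposes as weight, placebo effect and checking the dampers. That is fair, and it is one reason why the point is minor. The objective still asks for effects of the orthosis, and an upper bound answers that only loosely.

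**Conclusion.** The point holds as a minor one. The adverse event form does not capture device, condition or onset time, and no other required record does so for an event. Investigator-recorded events therefore cannot be reliably assigned to orthosis or sham. For these events a per-patient prevalence is an upper bound for the orthosis: 15% would fit anything from 0% to 15%.

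That range needs no assumption about how the devices relate. It would be tempting to go further and say that the reported figure overstates the orthosis rate about 1.9-fold (15/7.8). That ratio rests on equal and independent rates, applied to a percentage given only as an example. If the same patients reacted to both devices the ratio would be 1.0. It should not be used as an estimate.

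The endpoint is secondary and descriptive, with no test or threshold attached. The sample size, power and alpha are unaffected.

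**What to change.** 1. Add two fields to the form in Appendix II and to the CRF: condition at onset (baseline, sham, orthosis, after removal) and time of onset. Add them to the field list in Section 7.3.7.
2. In Section 9.2 under Potential adverse effects, replace the single prevalence per patient by the number and percentage of patients with each effect on the orthosis, on the sham and on both, drawing on the form and the D-QUEST answers.
3. List events that arise after removal separately, with the order in which the devices were worn.

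The cost is two form fields and one further split in a descriptive table, with no extra visits or patients. One limit remains: an effect that appears after the second device, on an arm that has worn both, may still not be attributable to either. Listing it with the device order shows that uncertainty without removing it.

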## 9.3 Other analysis

Tremor amplitude will be analyzed separately for the wrist flexion-extension and forearm pronation-supination, by making use of the data collected on both IMU sensors. This will also be used to evaluate tremor amplitude reduction per DoF, and per task.

Moreover, the health-related quality of life – using the EQ-5D-5L – will be used to determine if the perceived quality of life could have effect on the patient satisfaction from the secondary study parameter(s). A sub-analysis per category (*Mobility/Self-care/Usual Activities/Pain & Discomfort/Anxiety & Depression*) will be assessed per participant compared to the results obtained from D-QUEST.

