## 3. Inclusion of patients

The next step requires a visit to the hospital; this appointment will last for a maximum of one hour and takes place at the neurology department of the Reinier de Graaf hospital in Delft. Time will be taken to make the patient feel at ease, to make sure that the patient is not nervous or stressed which may increase tremor severity. The patient is allowed to drink something at this moment (caffeine and alcohol free). This is also when the procedure will be explained and allows a moment for the patient to ask questions. During this appointment, patients will be asked to perform the 7 selected TETRAS tasks (see Section 7.3.4), which will be videorecorded. Two synchronized webcams will record the tasks, which will be done for both the left and the right side. The IMU sensors will be attached on the wrist and hand to record the motion data (see Section 7.3.3). If the patient seems suitable for testing the orthosis, the IMU and video recordings will be used to indicate the tremor severity of the patient without orthosis (baseline).

The hand and upper arm circumference will also be measured by the investigator, these can later be used to select the correct size of the orthosis (S, M, L). If, after this step, the judgement can be drawn that the patient is suitable for the study, meaning that all inclusion- and exclusion criteria (see Section 4.2 and 4.3) are fulfilled, the assessment with the orthoses will directly follow. In preparation for this intervention, it will be determined which arm will be tested, including which size. If only one side turns out to be eligible (left or right), then that side shall be used to test the intervention. If both sides are eligible, the dominant arm as defined by the patient shall be used.

After the TETRAS tasks in baseline condition, the video recordings will be assessed by the principal investigator, where tremor severity and dominant tremor DoF is evaluated.

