## 7.3.3 Sensor placement and amplitude assessment

The investigator attaches the IMU sensors (Xsens MTw Awinda), which record motion data, to the subjects' wrist and hand. The first sensor is attached to the middle and ring finger with a Velcro strap. The second sensor is attached ventral side of the wrist, also with a Velcro strap. See Figure 5.

*Figure 5:* Placement of Xsens motion sensors on the ventral side of the wrist and the middle and ring finger

Hereafter, the arm motion, and also the tremor amplitude, can be recorded when the investigators enable the sensors in the software package, which includes APIs for connecting with their hardware. This motion data will only be collected while performing different movements and postures as explained below.

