## 7.3.4 Tremor severity assessment using TETRAS

The principal investigator will quantify the tremor severity using the TETRAS scale. The principal investigator is adequately trained to carry out this assessment. To minimize investigator bias, a second opinion from an independent neurologist will be consulted. These movements and postures are derived from the TETRAS scale  and patient will be asked to perform them for 30 seconds:

- **Eating with a spoon:** Using a spoon to bring peas from a bowl on the table to the mouth. This is an adaptation from the TETRAS scale, as it usually does not specify which solids or liquids must be used to assess eating with a spoon.
- **Drinking from a cup:** Bringing a cup (8 cm tall, filled with water to 1 cm from top) from the table to the mouth to drink water.
- **Pouring:** Pouring a water filled plastic cup (8 cm tall, filled with water to 1 cm from top) into another cup (8 cm tall) that is unsupported on the table.
- Forward outstretched posture: Subjects will bring their arms forward, slightly lateral to midline and parallel to the ground. The wrists should also be straight and the fingers abducted so that they do not touch each other (Figure 6).
- Lateral "wing beating" posture: Subjects will abduct their arms parallel to the ground and flex the elbows so that the two hands do not quite touch each other and are at the level of the nose. The fingers are abducted so that they do not touch each other (Figure 6).

Figure 6. Forward outstretched posture

Lateral wing beating posture

- **Finger-nose-test:** Subjects extend only their index finger. They then touch the examiners finger located to the full extent of their reach, which is located at the same height (parallel to the ground) and slightly lateral to the midline. Subject then touch their own nose (or chin if the tremor is severe) and repeat this back and forth.
- Archimedes spiral: Subjects are asked to copy an Archimedes spiral using a ballpoint pen that approximately fills an A6 sheet of paper (Figure 7). The lines of the spiral should be approximately 1.3 cm apart. The pen should be held in such way that no part of the limb touches the table.

*Figure 7.* Archimedes spiral. The patient will be asked to draw a spiral between the lines, connecting the two dots.

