## WRIST FLEXION/EXTENSION (WFE)

For flexion/extension of the wrist joint, we take the knuckle that is furthest from the wrist as a reference point. Here too, the FFE can cause difficulties. Measure the largest absolute distance you observe.

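### Section 9.3 promises a separate wrist flexion/extension amplitude, but a finger sensor and a wrist sensor can only give wrist and finger motion combined

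*Protocol*

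**What the plan says.** Protocol section 9.3 plans a per-joint analysis: "Tremor amplitude will be analyzed separately for the wrist flexion-extension and forearm pronation-supination, by making use of the data collected on both IMU sensors". The same data are to give the reduction per degree of freedom and per task.

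Section 7.3.3 fixes the two sites: "The first sensor is attached to the middle and ring finger with a Velcro strap" and "The second sensor is attached ventral side of the wrist, also with a Velcro strap". Section 7.3.1, under the inclusion visit, describes the placement differently: "The IMU sensors will be attached on the wrist and hand to record the motion data".

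Section 9.1 reads the co-primary amplitude from the distal sensor alone: "Tremor amplitude is measured during the performed tasks by taking the data from the IMU that is attached to the fingers". The next paragraph of that section says that the TETRAS rating and "tremor amplitude of the hand are the co-primary endpoints". Section 7.1.1 calls the same measure an overall amplitude per task.

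Section 1 lists finger flexion/extension as its own degree of freedom. It says that the dampers act on wrist flexion/extension and forearm pronation/supination, and that the frame restricts radial/ulnar deviation. It claims no effect on the fingers. Section 4.2 asks for a predominant forearm or wrist tremor with only minor shoulder, elbow and finger influence. For visual rating of wrist flexion/extension, Appendix I says: "we take the knuckle that is furthest from the wrist as a reference point. Here too, the FFE can cause difficulties".

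**The concern.** Measuring one joint with two sensors needs a sensor on each of the two segments that meet there. For the wrist these are the forearm side and the hand. Here the distal sensor is one joint further out, on the fingers, so the recorded difference spans the wrist and the finger joints.

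One of these joints is damped and the other is not said to be. A per-joint reduction reported as wrist flexion/extension would mix the two, and a reader could take it as evidence, favourable or not, about the wrist damper. The sites are fixed in the protocol, so a later analysis plan cannot recover the motion of a segment that was never recorded.

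**Working it through.** **Inputs.** Sensor sites: section 7.3.3. Damped joints: section 1. Finger tremor permitted at entry: section 4.2. Expected amplitude reduction of more than 60%: section 2.1. That figure is for overall amplitude; applying it to the wrist is my assumption. The documents give neither the share nor the phase of finger tremor, so the values below are assumed.

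**The plan's own figure.** No number is planned for the per-joint analysis. The one computed design figure, the sample size in section 4.4, reproduces: dz = 4/√(25 + 25 − 2·0.5·25) = 0.8, two-tailed alpha 0.0125, n = 21, power 0.810. It does not depend on this point.

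**Step 1, geometry.** Let W be the wrist oscillation and F the finger-joint oscillation. The motion of the finger sensor relative to the wrist sensor is W + F. That is one measured quantity for two unknowns, so W is not identifiable. The placement figure is not available, but any site on the fingers lies beyond the knuckles, so the exact site does not matter.

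**Step 2, size if the two oscillations are independent.** Take W = 5 units RMS at baseline and 2 with the orthosis (a true 60% reduction), with F unchanged. Apparent reduction = 1 − √(2² + F²)/√(5² + F²).
- F = 0: 1 − 2/5 = 60%
- F = 1: 1 − √5/√26 = 1 − 2.236/5.099 = 56%
- F = 2: 1 − √8/√29 = 1 − 2.828/5.385 = 47%

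**Step 3, dependence on phase.**
- In phase, 1 − (2 + F)/(5 + F): F = 1 gives 1 − 3/6 = 50%; F = 2 gives 1 − 4/7 = 43%.
- In antiphase, 1 − |2 − F|/(5 − F): F = 1 gives 1 − 1/4 = 75%; F = 2 gives 1 − 0/3 = 100%.

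For the same true 60%, the reported value can fall on either side of it.

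**Step 4, pronation/supination.** The wrist sensor can record forearm axial rotation, so the finger argument does not apply here. In the forward outstretched posture (section 7.3.4), taking the elbow as straight, shoulder axial rotation and forearm rotation share nearly one axis. There is no upper-arm sensor to separate them. This concerns one of the seven tasks.

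**Step 5, the co-primary.** Section 9.1 names the finger sensor as the source, section 7.1.1 defines an overall amplitude, and section 7.3.5 lets the sensors stay in the same places across conditions. The paired contrasts therefore compare like with like. What remains is that sections 7.3.1, 7.3.3 and 9.1 use hand and finger for the same site.

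**The case against.** The strongest reply is that this is a small matter. Section 9.3 is headed as other analysis, and none of the four Bonferroni-corrected comparisons in section 4.4 is per joint. Eligibility keeps finger tremor minor. The knuckle rule in Appendix I belongs to visual rating and sets no sensor site. All of this stands and limits the weight of the point. It does not rescue the analysis as described: minor influence is not absence, and an exploratory result still should not carry the name of a quantity that it does not measure.

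Some stronger readings are tempting but not supported:
- A reader might infer that both sensors are misplaced. The wrist sensor is a sound proximal reference; only the distal site causes the difficulty.
- A reader might infer that the wrist reduction is always understated. That holds for independent or in-phase finger motion that the orthosis leaves unchanged; antiphase motion reverses it.
- A reader might push the size further. Finger tremor of 3 units would give 1 − √13/√34 = 38%, but that is 60% of the wrist tremor (3/5) and hard to square with the minor influence required at entry.
- A reader might see a conflict between strapping two fingers together and the posture instruction "The fingers are abducted so that they do not touch each other". The documents point to no consequence for the analysis.

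**Conclusion.** The point holds for the wrist flexion/extension part of section 9.3. With the sensor sites of section 7.3.3, that amplitude is a combined wrist and finger amplitude, and the wrist-specific reduction is not identifiable. This follows from the placement and needs no numerical assumption.

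The size and direction of the error do rest on assumptions. For a true 60% reduction and unchanged finger tremor of 1 or 2 units against 5 at the wrist, the apparent value is 56% or 47% if the oscillations are independent. At 1 unit it runs from 50% (in phase) to 75% (antiphase).

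For pronation/supination the difficulty is confined to the outstretched posture, and exclusion of dominant shoulder rotation tremor (section 4.3) reduces it. A reader might infer that the co-primary amplitude is biased or invalid; the documents do not support that. It is openly read at the fingers, at a constant site within each patient, so only its name needs correcting.

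**What to change.** 1. Leave the sensor sites as they are. The finger sensor also supplies the co-primary amplitude, so moving it would change that measurement site in a study that, by section 3, began in March 2022. Data before and after the move could not be pooled. The hand piece may also leave little room proximal to the knuckles (section 6.5).
2. In section 9.3, rename the wrist output as combined wrist and finger flexion/extension, and state that no conclusion will be drawn about wrist flexion/extension alone.
3. For the forward outstretched posture only, report wrist-sensor axial rotation as combined forearm and shoulder rotation, or leave that task out of the pronation/supination analysis.
4. Align sections 7.3.1, 7.3.3 and 9.1 so that the distal site is the fingers throughout and the co-primary is called tremor amplitude at the fingers.

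The cost is a wording amendment. No data, sample size or primary test changes. What is given up is a wrist-only claim that the recordings could not support, and, if the second option in item 3 is taken, one task in an exploratory analysis.
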